10.5.3.3 Edmonton Frail Scale (EFS)

Frailty is a medical syndrome with multiple causes and contributors that is characterized by diminished strength, endurance, and reduced physiologic function that increases an individual's vulnerability for developing increased dependency. The Edmonton Frail Scale assesses nine domains of frailty including a cognition evaluation (i.e. hand-draw a face clock), functional performance (i.e. timed get up & go test), general health status, functional independence, social support, medication usage, nutrition, mood, and continence.^[11] It can be administered in 5-10 minutes and is scored from 0 to 17. A higher score indicates a higher degree of frailty, scores 10+ in the severe range. The total test score will be recorded on the eCRFs. A sample copy of the scale can be found in Appendix D.

10.5.4 Blood Samples

Blood sample collection can be completed after informed consent has been obtained. The blood sample can be collected at Baseline, before surgery, or at the start of the surgery visit. If the blood sample is taken after the patient has been sedated and anesthesia induction begins, the blood sample should be taken from the opposite arm from which the intravenous therapy infusion of propofol was administered. The blood sample should be taken as soon as possible, but is required to be taken before intubation or the first surgical incision is made (whichever comes first).

Blood samples to assess the levels of the following will be collected and documented in the eCRF:

- Albumin (gm/dL)
- Hemoglobin (gm/dL)
- Total cholesterol (mg/dL)
- Total protein (gm/dL)

10.6 Surgery

The following sub-sections outline the required procedures and data collection during the surgery.

10.6.1 Pregnancy Screening

Due to the potential risk the surgery and anesthesia administration might pose, pregnant women should not take part in this study. It is expected that female subjects of child-bearing potential (i.e. not post-menopausal or surgically sterile) will be screened for pregnancy according to standard institutional policies before the surgery visit. If standard screening is not in place, then a urine or blood pregnancy test must be administered, and results confirmed as close to the time the surgery begins as possible to confirm they are not pregnant.

If the Baseline and Surgery visits take place on separate days, female subjects must agree to not become pregnancy during the study by using a medically acceptable method of birth control. If a subject does become pregnancy, there may be risks to the subject or to their unborn child that are not yet known. Subjects must notify the study doctor immediately if they think they are pregnant or if they become pregnant during the study. If in the Investigator's opinion enough time has passed between the test and the time of surgery, the subject may be required to undergo another pregnancy test.

Site personnel are responsible for the following:

- Documenting all available information regarding the pregnancy in the source documents and notifying Medtronic study personnel
- Notifying the IRB per the study site's requirements

Exiting the subject from the study and completing the appropriate eCRF(s) according to Section 10.10.1.

10.6.2 Sensor Application

Prior to any anesthesia administration and following preparation of the skin of the subject's forehead, a bilateral BIS™ sensor will be applied. The BIS™ data collection will start with sensor application and continue throughout the entire duration of the surgery.

One or more Nellcor™ sensors may also be applied at this time to collect pulse oximetry data. The sensor(s) should be placed on a finger on the opposite arm in which the intravenous therapy line is located or can also be placed on a big toe. The precise location of each sensor will be captured in the eCRF.

10.6.3 Induction Period

During the induction procedure, subjects will be pre-medicated per institutional guidance. All pre-medications, doses, and times of administration will be recorded in the eCRFs.

Prior to induction, subjects will be assessed using the Modified Observer's Assessment of Alertness/Sedation Scale (MOAA/S) which can be referenced in Appendix A.

A slower induction of anesthesia will be achieved by setting a lower initial target propofol dose and making an incremental increase in the targeted dose. This is a conservative approach which maintains consistency across all study subjects and will ensure safety of the elderly patients included in the study, which should also closely align with standard institutional practices. The propofol will be administered using target-controlled infusion (TCI) pump, and the initial targeted effective site concentration (Ce) will be half of the effective site propofol concentration dosage based on drug Instructions for Use (IFU) based on the subject's body mass used for induction. The TCI will calculate the initial bolus and infusion rate required to rapidly achieve and maintain this drug level based on propofol's population pharmacokinetics using the Schnider Model. At this step, the depth of anesthesia will be assessed using MOAA/S after an equilibrium time of approximately 5 minutes (from the start of propofol infusion.) After this initial step, the target effect site concentration is subsequently adjusted in an attempt to maintain the desired level of sedation and three-quarters of the Ce will be administered. This second step will also require depth of anesthesia assessment using MOAA/S after an equilibrium time of approximately 5 minutes. Lastly, the final/full Ce dose of the propofol will be administered, and the MOAA/S will be assessed after another equilibrium time of 5 minutes is reached. The specified induction period will last approximately 15 minutes in order to record and monitor the BIS values, EEG readings, and MOAA/S scores across the anesthetic agent introduction into the subject.

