A Pocket Guide for Clinicians of the BIS™, several clinical situations can influence the accuracy of the BIS™ value as an indicator of anesthetic hypnotic effect. Four key areas include the influence of muscle tone (EMG) from the forehead muscles; electrical and mechanical artifacts from medical devices; abnormal EEG states; and certain anesthetic agents and adjuvants – which can all lead to elevated BIS™ values. Serious clinical conditions – which may require a prompt response – have been associated with the sudden appearance of low BIS™ values. BIS™ responses are similar when most, but not all, anesthetic agents are administered in increasing amounts. Specifically, BIS™ responses to typical hypnotic agents (midazolam, Propofol, thiopental, isoflurane) were similar^[3,4]. However, halothane has been found to have higher BIS™ values at an equipotent minimum alveolar concentration dose^[5]. Further, BIS responses to ketamine administration are atypical^[6,7]. In addition, BIS™ responses to administration of analgesic agents – including opioid analgesics and nitrous oxide – depend on the level of concomitant stimulation.

A significant correlation between BIS™ Index values and reduction in whole brain metabolic activity due to increasing anesthetic effect was measured using positron emission tomography^[8]. Thus, factors other than drug administration that can influence brain metabolism (e.g., alterations in temperature or physiologic homeostasis) may also produce changes in the BIS™ Index.

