10.5.1 Demographic and Medical History

Demographic details (i.e., gender, weight, height, age, skin pigmentation), and medical history including primary and secondary diagnosis will be transcribed into the eCRF.

There are no medication/therapy restrictions in the study unless they are investigational and may confound the study results, in which case, prior approval would be needed from Medtronic. All prescription and over-the-counter medications taken within 14 days prior to screening will be collected and transcribed into the eCRF. The name of the medication, dose, and frequency and start and stop dates will be recorded.

If the baseline procedures occur on a separate date from the surgery visit, the subject should identify to the study team, the name and contact information of an individual that can be contacted in case the subject cannot be reached for any reason. This individual may be asked how the study subject may be reached, and about the subject's health status.

Subjects who are completing the baseline and surgery requirements on the same day will not be required to provide a contact person as there is no follow-up period beyond surgery.

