10.6.5 Data Collection

The start time of any drug infusion, target effect-site concentrations, infusion rate, the start time of the assessment including BIS value prior to MOAA/S assessment, and MOAA/S assessment will be recorded in the eCRFs. Any adjustments to the infusion rate and time of adjustment will be recorded, and any changes to subject management during the procedure will be noted on the eCRFs.

The MOAA/S score, time of and main procedural event will be recorded on the eCRFs.

The anesthetic drugs, muscular blocking agents (NMBA), NMBA reversal drugs, anti-nausea drugs, and drugs that reduce pain the drug, dosage, and time will be recorded on the eCRF.

Blood pressure, EtCO₂, SpO₂, pulse rate, respiration rate, end-tidal anesthetic gas, FiO₂%, EtO₂%, and temperature will be gathered from the hospital computerized database, and digital records will be provided to Medtronic. BIS values and EEG data will be recorded with a USB storage device connected to the BIS™ complete monitor. The BIS data file labeled with patient ID will be provided to Medtronic.

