7.2.1 Statistical Method

Descriptive statistics will be used to summarize study outcomes. Subjects with valid recorded data from the study device (EEG signals) and a completed eCRF will be included in the primary analysis.

The relationships between BIS parameters, age, physical and cognitive state, and depth of anesthesia in patients undergoing surgery under general anesthesia will be assessed. Also, the relationship between BIS and MOAA/S will be examined by subjects under 65 and by subjects over 65 years old. Pearson's correlation or Spearman's rank correlation will be calculated as appropriate. Continuous variables will be evaluated using analysis of variance (ANOVA) or nonlinear E_{max} model, and categorical variables will be evaluated using the chi-square or Fisher's exact test, as well as multivariate logistic regression with age as an explanatory factor. A P-value of less than 0.05 is considered statistically significant unless otherwise specified.

Specifically, for the primary objective, a polytomous logistic regression model will be employed to assess the relationship between the MOAA/S scale and the BIS score/age groups (18-64 vs. 65+). The interaction between age and BIS score will be included. Another dichotomous logistic regression model will be utilized as well, when the MOAA/S scale is classified as responsive (scale of 2, 3, 4, and 5) and non-responsive (scale of 0 and 1).

The BIS scores at various time stamps (e.g., first response, extubation, etc) will be compared between the two age groups.

A simplified Sigmoid E_{max} model will also be used to analyze the relationship between the BIS™ index and loss of responsiveness through the probability of response curves. The values of BIS™ at which 50% (BIS_{50}) and 95% (BIS_{95}) of subjects are unresponsive, and their 95% confidential intervals will be derived. The systematic variance between groups will be evaluated.

The model is as follows:

$$P = \frac{e^{a+bX}}{1 + e^{a+bX}}$$

where P is the probability of "unresponsive", X is the explanatory variable (BIS™ value or anesthetic agent concentration on the log scale), and a & b are model parameters.

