For each age subgroup, one can estimate the BIS™ value and the effect-site concentration at which 50% subjects are unresponsive, i.e., BIS_{50} and EC_{50} respectively. The corresponding 95% confidence intervals and standard errors for the estimates will be derived. The same evaluation will be performed for BIS_{95} , at which 95% subjects are unresponsive. The systematic variance between groups will be evaluated accordingly.

Multivariate logistic regression model will be used to study the effects of other baseline covariates (gender, blood panel, physical and cognitive states).

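### Co-administered sedatives and opioids are recorded but enter no SAP model, so an age difference in their use would confound the EC50 contrast and, for some drugs, the BIS50 contrast

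*Protocol*

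**What the plan says.** **Drug exposure (Protocol).**
- 10.6.3 standardises the propofol steps but not what accompanies them: "During the induction procedure, subjects will be pre-medicated per institutional guidance". The stepped scores come from the same period: "The specified induction period will last approximately 15 minutes in order to record and monitor the BIS values, EEG readings, and MOAA/S scores".
- 10.5.1: "There are no medication/therapy restrictions in the study unless they are investigational and may confound the study results". Such drugs need the sponsor's agreement beforehand. Exclusion criterion 4 (9.4) removes chronic opioid, narcotic or analgesic use that may blunt response to analgesics. It does not address perioperative drugs.
- The data are captured. 10.6.3: "All pre-medications, doses, and times of administration will be recorded in the eCRFs". 10.6.5: "The anesthetic drugs, muscular blocking agents (NMBA), NMBA reversal drugs, anti-nausea drugs, and drugs that reduce pain the drug, dosage, and time will be recorded".

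**What these drugs may do to BIS (Protocol 7.5.5).** Among the influences on the accuracy of BIS are "certain anesthetic agents and adjuvants – which can all lead to elevated BIS™ values". The same section says that unconscious people may read above 60 with some sedative and analgesic combinations. It calls ketamine responses atypical and makes opioid and nitrous oxide responses depend on concomitant stimulation. It also reports similar BIS responses to midazolam, propofol, thiopental and isoflurane.

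**Models (SAP 7.2.1).** The leading model is described thus: "a polytomous logistic regression model will be employed to assess the relationship between the MOAA/S scale and the BIS score/age groups (18-64 vs. 65". An age-by-BIS interaction is added. A dichotomous version of MOAA/S follows. A sigmoid curve with a single explanatory variable (BIS, or log agent concentration) gives BIS50 and EC50 in each age subgroup. Then: "Multivariate logistic regression model will be used to study the effects of other baseline covariates (gender, blood panel, physical and cognitive states". No drug term appears in any of these.

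**The concern.** The study asks whether the relation between BIS and depth of anesthesia depends on age, so that the index can be improved for the elderly (Protocol 4.1, 4.2). Age is not randomised, so anything that differs by age and affects response is a candidate confounder. A co-administered sedative or opioid is an obvious one.

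The two estimands are exposed differently. EC50 is indexed to propofol concentration alone, so any co-drug that deepens sedation lowers the apparent propofol EC50 in the group that receives more of it. BIS50 is indexed to the EEG reading. It is materially affected only if the co-drug separates BIS from response.

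At stake is whether part of an apparent age effect, or the lack of one, reflects local premedication habits.

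**Working it through.** **1. The plan's own yardstick.** No figure in the plan is disputed here. SAP section 6 bases its power statement on a 5-point BIS shift with SD 10. With 200 subjects split 35%/65% (70 and 130) and two-sided 0.05 (sidedness is assumed):
- SE = 10 × √(1/70 + 1/130) = 1.48
- 5/1.48 − 1.96 = 1.41, so power is 92.1%. The SAP's figure of more than 90% reproduces.

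Protocol 5.1 plans up to 100 subjects (35 and 65) and makes no power claim. The same calculation would give 66.5%. The 5 points serve below only as a scale for the bias.

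**2. Assumed inputs.** The documents give no drug use by age and no drug effect sizes. Let p be the proportion receiving a co-drug in each age group, r the proportional fall in propofol EC50 that it causes, and s the number of BIS points by which it raises the reading at loss of response. No true age effect is assumed.

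**3. Closed form.** Each group's mean log EC50 moves by p × log(1 − r), so
- spurious EC50 ratio (65+ over 18-64) = (1 − r)^(p_old − p_young)
- spurious BIS50 shift ≈ s × (p_old − p_young)

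With higher use in the younger group:

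| Gap in use | EC50 ratio, r = 10% to 40% | BIS50 shift (absolute), s = 2 to 10 |
|---|---|---|
| 0 points | 1.00 | 0 |
| 10 points | 1.01 to 1.05 | 0.2 to 1.0 |
| 30 points | 1.03 to 1.17 | 0.6 to 3.0 |
| 50 points | 1.05 to 1.29 | 1.0 to 5.0 |

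For example, 0.6^(−0.5) = 1.29. If use is higher in the elderly the exponent changes sign: 0.9^0.1 = 0.99 and 0.6^0.5 = 0.77, and the BIS50 shift changes sign as well. If s = 0, the closed-form BIS50 shift is 0.

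**4. Simulation.** 100 subjects, three relative propofol steps (0.5, 0.75, 1.0), one binary co-drug, logistic models with subject-clustered standard errors, 400 runs per scenario. Age enters as a main effect only, which simplifies the SAP's interaction and subgroup curves. Shifts are 65+ minus 18-64. False positives are age effects with p < 0.05.

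| Use, young/old | r, s | EC50 ratio | BIS50 shift | False positives, EC50 / BIS50 |
|---|---|---|---|---|
| 50%/50% | 20%, 5 | 1.00 | 0.0 | 5% / 5% |
| 80%/50% | 20%, 0 | 1.07 | −0.7 | 12% / 5% |
| 80%/50% | 20%, 5 | 1.07 | −2.1 | 17% / 15% |
| 80%/30% | 20%, 0 | 1.13 | −1.0 | 32% / 6% |
| 80%/30% | 30%, 10 | 1.21 | −6.7 | 62% / 68% |

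The simulated BIS50 shifts run a little beyond the closed form because simulated BIS is a noisy reading of depth, which leaves a small shift even at s = 0. At 80%/50%, −0.7 from that source and −0.3 × 5 = −1.5 from decoupling account for the −2.1.

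**5. With the fix.** Adding one premedication indicator brings the EC50 ratio to 0.995 to 1.006, the BIS50 shift to −0.4 to +0.3 points, and false positives to about 4% to 8% in every 100-subject scenario. This rests on a single binary drug. Real dose and timing would be captured less completely, and a site term was not simulated.

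**6. Restricting to subjects without co-drugs.** At an assumed 80%/40% use, 20% of 35 = 7 younger and 60% of 65 = 39 older subjects would remain. Seven is too few for a useful BIS95 or EC50.

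**The case against.** A reader might infer that the SAP, followed as written, attributes a drug effect to age. The documents do not support that.

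- **No age difference in use is documented.** Protocol 4.1 says that older patients are more sensitive and usually need less medication for a given effect. That concerns sensitivity and dose, not how often premedication is given, and a lower dose in a more sensitive patient may have the same effect. It also suggests a true EC50 ratio below 1, so heavier use in the young would mask an age effect rather than create one. This stands: size and direction are unknown.
- **Protocol 7.5.5 cuts both ways.** It reports similar BIS responses to midazolam and propofol, and limits its remark on values above 60 to some settings and combinations. Nor does the Protocol name the premedication classes or say that opioids are given during the steps. This stands too: the BIS50 bias is conditional on decoupling.
- **Existing provisions.** Exclusion 4 already deals with chronic opioid and analgesic use, so extending the home-medication history is a separate matter and is not pursued here. SAP 7.3 would examine baseline and procedural variables if sites differ, but that concerns sites, not the age contrast.
- **Feasibility study and flexible SAP.** Protocol 14.1 disclaims power, and the recorded drugs allow later adjustment. But bias does not depend on power, SAP 7.2.1 applies p < 0.05, and the SAP's introduction foresees use in regulatory submissions. Choosing the adjustment after seeing the age contrast is what pre-specification is meant to avoid.
- **The unadjusted contrast has a meaning of its own:** it describes age groups under local practice. That is a reason to report both, not to omit the adjusted one.

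**Conclusion.** The omission is a matter of text: drug, dose and time are collected, co-drugs are left to local practice in the period that yields the stepped scores, and no model in SAP 7.2.1 uses them. The consequence is conditional. If use or dose differs by age group, the EC50 contrast is confounded by any co-drug that deepens sedation. The BIS50 contrast and the BIS-by-age terms are confounded materially only where the co-drug alters the BIS-response relation.

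On the assumed inputs the bias runs from none to sizes comparable with the SAP's 5-point shift, the upper end needing both a 50-point gap in use and strong drug effects. Confidence is high in the gap and the mechanism, and low in any particular magnitude or sign. The gap should be closed before the data are analysed, because the remedy uses data already in the eCRF.

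**What to change.** In SAP 7.2.1:
- Pre-specify terms for sedative premedication (yes/no), opioid given before the MOAA/S score (yes/no, from the recorded times) and site. Put them in the polytomous and dichotomous models and in the age contrasts of EC50 and BIS50. Site belongs there because premedication follows institutional guidance and Protocol 5.1 has two centers.
- Report adjusted results beside unadjusted ones.
- Tabulate co-drug use by age group, so that the reader can see whether the condition for bias is met.
- Show results in subjects without co-drugs descriptively only, and only if numbers allow.

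The cost is one to three degrees of freedom, slightly wider intervals and some SAP wording. The SAP still elaborates Protocol version 4 (200 subjects, about five centers) and needs revision anyway. No new data collection and no change to clinical management is involved.

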10.6.4 Maintenance & Recovery

After the specified induction period, anesthesia will continue according to standard practice/institutional guidance.

At the beginning of induction, the depth of anesthesia will be assessed to ensure a MOAA/S of 0 has been obtained.

In addition, the time of the following assessments will be collected during the surgery:

- Start of induction of anesthesia
- Intubation
- Surgical Incision
- Skin Closure
- End of The Surgery
- Extubation
- Immediately Prior To BIS™ Sensor Removal

10.6.5 Data Collection

The start time of any drug infusion, target effect-site concentrations, infusion rate, the start time of the assessment including BIS value prior to MOAA/S assessment, and MOAA/S assessment will be recorded in the eCRFs. Any adjustments to the infusion rate and time of adjustment will be recorded, and any changes to subject management during the procedure will be noted on the eCRFs.

The MOAA/S score, time of and main procedural event will be recorded on the eCRFs.

The anesthetic drugs, muscular blocking agents (NMBA), NMBA reversal drugs, anti-nausea drugs, and drugs that reduce pain the drug, dosage, and time will be recorded on the eCRF.

Blood pressure, EtCO₂, SpO₂, pulse rate, respiration rate, end-tidal anesthetic gas, FiO₂%, EtO₂%, and temperature will be gathered from the hospital computerized database, and digital records will be provided to Medtronic. BIS values and EEG data will be recorded with a USB storage device connected to the BIS™ complete monitor. The BIS data file labeled with patient ID will be provided to Medtronic.

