7.5.1 BIS™ Complete Monitoring System

The BIS™ Complete Monitor is an easy to use microprocessor-based EEG monitor. The BIS™ Complete Monitor reports a BIS value by acquiring up to two channels of EEG from sensors attached to the patient's forehead and performing the computations necessary to produce the BIS™ Index. The BIS™ Index is then numerically displayed for the clinician's use. The BIS™ Complete Monitoring System consists of the following components as shown below in **Figure 1**:

The influence of age on EEG signals and consciousness during anesthesia (TIARA) Clinical Investigation Plan

Version 5.1

Page 18 of 65

Form

Medtronic

- BIS™ Complete Monitor
- BISx4™ (BISx4 will be used in this study)
- Patient Interface Cable (PIC)
- BIS™ Bilateral Sensor
- Detachable Power Cord

Figure 1: The BIS™ Complete Monitoring System. 1 - Monitor Interface Cable; 2 - BIS™ Monitor; 3- BIS™ bilateral sensor will be used; 4- Patient Interface Cable (PIC); 5- BISx4™ (LoC 4 Channel)

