7.7 Product Training Materials

All investigators and study staff members will be trained by the sponsor. The training will be performed prior to site activation and the recruitment of the first subject. Investigators or staff members are not permitted to perform any activity in the study before training is completed and correctly documented. Training will include at least the following topics:

- Study procedures
- Informed consent procedures and documentation
- Adverse Events (AEs), Safety Events, Device Deficiencies (DDs) and the reporting procedures of these events
- Good Clinical Practice (GCP)
- Study device management
- Case Report Form (CRF) completion
- Overview of the physical and cognitive assessment procedures
- Overview of ISO14155

It is the responsibility of the Principal Investigator (PI) at each participating site to ensure any staff performing tasks related to the clinical trial (e.g., Study Coordinators, Study Nurses, Sub-Investigators, etc.) have been appropriately trained, their training documented and included on the Delegation of Authority Log.

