Examples of study deviations include but are not limited to:

- Failure to obtain proper Informed Consent
- Failure to collect required study data (e.g. MOAA/S Scores, patient assessments, BIS raw signals)
- Inclusion/exclusion criteria not met
- Missing required anesthesia administration documentation

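### The protocol does not require MOAA/S to be scored before BIS is read, so the outcome of the BIS-by-age model could lean towards its own predictor, mainly at score 5 versus 4

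*Protocol*

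**What the plan says.** Protocol 10.6.3 has MOAA/S assessed before induction and after each of three propofol steps. For these assessments, 10.6.5 states that "the start time of the assessment including BIS value prior to MOAA/S assessment, and MOAA/S assessment will be recorded in the eCRFs". The same section has BIS and EEG stored on a USB device. Section 7.5.1 says of the monitor: "The BIS™ Index is then numerically displayed".

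SAP 7.2.1 says that, for the primary objective, "a polytomous logistic regression model will be employed to assess the relationship between the MOAA/S scale and the BIS score/age groups", and adds: "The interaction between age and BIS score will be included". A second, two-category model contrasts scores 0 and 1 with scores 2 to 5.

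No section names the rater, separates the rater from the display, or says which of score and BIS value is written down first. The training list in 7.7 has "Overview of the physical and cognitive assessment procedures" but nothing on masking or order. The deviation examples in 10.9 cover missing MOAA/S scores, not scores given with BIS in view. The only mention of blinding, in 16.4, concerns subject names.

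**The concern.** Protocol 14.1 frames the primary question as the effect of age on the relation between BIS and depth of anesthesia. MOAA/S is the depth measure. If the rater knows BIS when choosing the score, outcome and predictor are no longer measured independently.

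Pairing the score with a BIS value from before the stimulus is sensible, since the stimulus can itself change BIS. But if someone reads that value at the bedside before the score is given, the number may be in the rater's mind at the moment of judgement. Three consequences are possible:

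- The age effect is diluted, if raters read BIS the same way at every age.
- It is inflated, if raters over-allow for age.
- The BIS slope is steepened, so that the index looks more accurate than it is.

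The data are meant to improve the index in the elderly, so the first two touch the purpose of the study directly.

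**Working it through.** The documents state no figure to reproduce. The check has two parts: where the scale allows influence, and how much it could matter.

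**1. Where judgement enters (Appendix A).** Scores 5 and 4 share one stimulus, the name in a normal tone, and differ only in how promptly the subject responds. Score 3 has its own stimulus (a loud or repeated call), with some latitude. Scores 2, 1 and 0 depend on whether prodding or a trapezius squeeze draws a response. Exposure is therefore greatest at 5 versus 4, smaller at 3, and small at the 0-1 versus 2-5 cut.

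**2. Size, by simulation.** From the documents: 65% aged 65 or over, n = 100 (Protocol 14.1), and four ratings per subject (10.6.3). All other inputs are assumptions:

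- BIS means 95/80/68/52, between-subject SD 5, within-subject SD 8.
- MOAA/S cuts at BIS 58/70/76/82/90 in the young and 5 points lower in the elderly, with subject SD 4 and rating SD 4.5 around the cuts.
- A fraction w of ratings is influenced. An influenced score moves at most one category towards the score BIS implies, and only within the permitted range (3 to 5, or 4 to 5).
- Raters read BIS in one of three ways: (a) one common reading for all ages, (b) allowing for twice the true age shift, (c) allowing for the true shift.

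Model, read as proportional odds, with E = 1 for the elderly: logit P(score > k) = b1·BIS + b2·E + b3·BIS·E − t_k. BIS at 50% is t_k/b1 in the young and (t_k − b2)/(b1 + b3) in the elderly. Their difference is the age shift at cut k.

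Large-sample results (120,000 subjects per setting; with w = 0 the shift is 5.01 at every cut):

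| Scores that can move | w | Mean shift (a) | Mean shift (b) | 5/4 cut (a) | 5/4 cut (b) |
|---|---|---|---|---|---|
| 3 to 5 | 10% | 4.8 | 5.2 | 4.6 | 5.3 |
| 3 to 5 | 20% | 4.6 | 5.35 | 4.2 | 5.7 |
| 3 to 5 | 30% | 4.4 | 5.5 | 3.8 | 6.0 |
| 5 versus 4 only | 30% | 4.7 | 5.3 | – | – |

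Under (c) the mean shift stays at 5.0. The BIS50 shift on 0-1 versus 2-5 stays at 5.0 throughout. With scores 3 to 5 movable and w = 30%, the BIS slope is 7%, 5% and 8% steeper under (a), (b) and (c), and the false interaction is −0.13 (a) or +0.10 (b) per 10 BIS points. At most 4.9% of scores change.

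Separate simulations agree. With the same model, 30% influence gave 4.43, 5.54 and 5.02 for scores 3 to 5, and 4.68 and 5.32 for 5 versus 4 only. Without the interaction, the last pair was 4.60 and 5.28.

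**3. Against sampling error at n = 100** (600 replicates): SD 1.1 for the mean shift, 1.4 at the 5/4 cut, 0.17 for the interaction and 6% for the slope.

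- Mean shift, w = 10%: 0.2/1.1 = 0.18 SD.
- Mean shift, w = 30%, scores 3 to 5: 0.6/1.1 = 0.55 SD (a) and 0.5/1.1 = 0.45 SD (b).
- Mean shift, w = 30%, 5 versus 4 only: 0.3/1.1 = 0.27 SD, or 0.4/1.1 = 0.36 SD with the 4.60 result.
- 5/4 cut, w = 30%, scores 3 to 5: 1.2/1.4 = 0.86 SD (a) and 1.0/1.4 = 0.71 SD (b).
- Interaction, w = 30%: 0.13/0.17 = 0.76 SD (a) and 0.10/0.17 = 0.59 SD (b).

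Sampling SD falls as 1/√n and the bias does not. A bias of 0.6 equals one SD at n = 100 × (1.1/0.6)² = 336, and a bias of 0.3 at n = 100 × (1.1/0.3)² = 1,344.

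**4. Sensitivity.** A cruder set-up used noisier scores, no interaction, outright replacement by the BIS-implied score, and 60 data sets of 100. The shift was 5.2 with no influence and 4.4 with 25% of scores 3 to 5 replaced; the 0-1 versus 2-5 shift stayed between 5.0 and 5.2. If scores at every level could be replaced, 25% gave 3.6, and 4.2 for the two-category model. The protection of that model therefore depends on the stimulus-defined levels being scored as defined.

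**The case against.** The strongest reply is that the plan is silent here and does not describe a bad practice. A reader might infer from 10.6.5 that the rater reads BIS and then scores. The text does not say so: it fixes which BIS value is recorded, not who reads it or where. Section 10.8 accepts data from automated instruments as source, so taking the value from the USB file is already allowed. Training material or worksheets that are not part of these documents may settle the order. All of this stands, but allowing the safer route is not the same as requiring it.

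Second, the effect is small, of unknown direction, and depends on assumed inputs, in a study that 14.1 calls an unpowered feasibility study. That also stands. Adding the check at the start of maintenance, where a score of 0 is expected, would lower the share of changed scores further (4.9% × 4/5 = 3.9%).

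Third, a reader might extend the point to other analyses. SAP 7.2.1 says: "The BIS scores at various time stamps (e.g., first response, extubation, etc) will be compared between the two age groups". First response is not among the timed events in Protocol 10.6.4, and BIS at extubation does not use MOAA/S, so the documents do not support that extension. Nor do they support one to BIS50 and BIS95, provided the SAP's unresponsive class there is the same 0-1 group.

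Fourth, scoring first cannot undo a glance at the display. This is true, and it limits what the fix can achieve.

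**Conclusion.** The point holds as a modest design improvement. As written, the plan can be followed exactly while the rater learns the predictor just before judging the outcome, and nothing in either document prevents that. The exposed analyses are the six-level model, its interaction, and correlations that use the six-level score.

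Even with 30% of ratings influenced, which nothing in the documents suggests, the bias in the mean age shift is about a quarter to a half of one sampling SD at n = 100. It may go either way, or vanish if raters allow correctly for age. The steeper BIS slope appears under all three readings, but its 5% to 8% is about the size of the 6% sampling SD. These figures rest on the assumed BIS distribution, cuts and noise, and on movement of one category at most. The documents do not show that any score has been or will be influenced. The case for acting is that prevention is cheap and that this bias would not shrink if the sample size were re-estimated upward, as 14.1 permits.

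**What to change.** In Protocol 10.6.5, state: *The rater records the MOAA/S score and the assessment start time before any BIS value is read for the eCRF. The paired BIS value is the last one before that start time, taken afterwards from the USB file.* This keeps the paired value before the stimulus and uses data already collected. Add a check of the monitor clock against the eCRF clock at sensor application. Turn the study display away from the rater where the rater is not managing the anesthetic.

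Optional: one yes/no eCRF item on whether the rater could see BIS, and a sentence in SAP 7.2.1 naming unmasked rating as a limitation of the six-level model and noting that the 0-1 versus 2-5 model is less exposed. A summary by visibility may have too few masked ratings to be useful.

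Cost: a short protocol and eCRF wording change, one clock check per case and a small matching program, with no extra staff. Pairing then depends on synchronised clocks, and masking will be incomplete where the rater belongs to the anesthesia team.
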